11.1.3. Secondary Efficacy Endpoint 1: Sensed Amplitude in the RA and RV

The efficacy of the INGEVITY+ Leads will be further be established by demonstrating that the leads provide clinically acceptable sensing amplitudes at three months post-implant.

11.1.3.1. Hypotheses

The following hypotheses will be used to evaluate Secondary Efficacy Endpoint 1 for each of the right-sided chambers:

Atrial leads

H_0 : P-wave sensed amplitude at three months post-implant ≤ 1.5 mV

H_a : P-wave sensed amplitude at three months post-implant > 1.5 mV

Ventricular leads

H_0 : R-wave sensed amplitude at three months post-implant ≤ 5 mV

H_a : R-wave sensed amplitude at three months post-implant > 5 mV

11.1.3.2. Sample Size for Secondary Effectiveness Endpoint 1

This endpoint will be evaluated separately for each of the two heart chambers. A sample size of 13 atrial leads (11 required for analysis plus 2 for attrition) and 9 ventricular leads (8 required for analysis plus 1 for attrition) is required for Secondary Effectiveness Endpoint 1. This sample size was calculated using a one-sample t-test, using SAS version 9.4 with the following assumptions:

Atrial leads:

- Expected performance = 3.5 ± 2.0 mV
- Performance goal = 1.5 mV
- Expected attrition/missing data = 10%
- One-sided significance level = 5%
- Power = 90%

Ventricular leads:

- Expected performance = 12 ± 6 mV
- Performance goal = 5 mV
- Expected attrition/missing data = 10%
- One-sided significance level = 5%
- Power = 90%

Note that the sample size for the study is not determined by this endpoint.

11.1.3.3. Statistical Methods for Secondary Efficacy Endpoint 1

All sensed amplitude data collected at the three-month follow-up visit that is available at the time of analysis will be included in the endpoint analyses.

Endpoint analysis will be performed separately for each heart chamber. A one-sided one-sample t-test will be performed, using an alpha equal to 5%. If the t-test is deemed to be inappropriate based on the data, then a data transformation or a non-parametric test will be performed. If the p-value for the one-sided test is less than 0.05, the null hypothesis will be rejected.

11.1.4. Secondary Efficacy Endpoint 2: Pacing Impedance

The efficacy of the INGEVITY Leads will further be established by demonstrating that the leads provide clinically acceptable pacing impedance at three months post-implant.

11.1.4.1. Hypotheses

The following hypotheses will be used to evaluate Effectiveness Endpoint 3 for each of the lead fixation types:

$$H_0: \text{Pacing impedance} \leq 300 \Omega, \text{ or Pacing impedance} \geq 1300 \Omega$$

$$H_a: 300 \Omega < \text{Pacing impedance} < 1300 \Omega$$

11.1.4.2. Sample Size for Secondary Effectiveness Endpoint 2

A sample size of 15 leads (13 required for analysis plus 2 for attrition) is required for Effectiveness Endpoint 3. This sample size was calculated using a one-sample t-test, using SAS version 9.4 with the following assumptions:

- Expected performance = $650 \pm 400 \Omega$
- Performance goals = 300Ω and 1300Ω
- Expected attrition/missing data = 10%
- One-sided significance level = 5%
- Power = 90%

Note that the sample size for the study is not determined by this endpoint.

11.1.4.3. Statistical Methods for Secondary Effectiveness Endpoint 2

All pacing impedance data collected at the three-month follow-up visit that is available at the time of analysis will be included in the endpoint analysis.

Two one-sided t-tests (TOST) will be performed, using an alpha equal to 5% for each test. If the TOST is deemed to be inappropriate based on the data, a data transformation or a non-parametric test will be performed. If both of the p-values for the two one-sided tests are less than 0.05, the null hypothesis will be rejected.

11.2. *Ancillary Analysis*

- Summary of turn count for all implanted and attempted leads
- Summary of the implant questionnaire including:
 - Lead handling
 - Lead maneuverability
- Summary of accessories used

- Summary of lead-related Adverse Events
- Summary of lead-related device deficiencies, including extension/retraction issues

11.3. ***General Statistical Methods***

11.3.1. **Analysis Sets**

For an INGEVITY+ lead to be eligible to contribute to endpoint analyses, it must be the final lead implanted or attempted per chamber during the initial procedure. Therefore, each subject may contribute up to two total INGEVITY+ leads to the endpoint analyses – one each for the right atrium and right ventricle. These leads will be called ‘endpoint leads’ in this section. The following analysis sets will be used for each endpoint.

Endpoint	Analysis Sets
Primary Safety Endpoint	All endpoint leads
Primary Efficacy Endpoint	All endpoint leads with 3-month visit PCT data
Secondary Efficacy Endpoint 1	All implanted endpoint leads with 3-month visit sensed amplitude measurements
Secondary Efficacy Endpoint 2	All implanted endpoint leads with 3-month visit pacing impedance measurements

11.3.2. **Control of Systematic Error/Bias**

Selection of subjects will be made from the investigator’s usual patient load. All patients meeting the eligibility criteria and having signed the ICF will be eligible for enrollment in the study.

11.3.3. **Number of Subjects per Investigative Site**

To avoid any center effect and bias, one center will not be authorized to implant or attempt more than 20% of the maximum number of subjects, without approval from BSC.

11.4. ***Data Analyses***

11.4.1. **Interim Analyses**

Analyses of adverse events and device deficiencies will occur at frequent intervals during the course of the study. Results of these analyses will be reviewed by the BSC Medical Safety Group to evaluate the safety of the subjects under study.

No formal interim analyses are planned for the purpose of stopping the study early for declaring safety or effectiveness. The hypothesis test for each endpoint will be performed when all applicable data for that endpoint has been collected.

11.4.2. Subgroup Analyses

Analyses will be performed for each endpoint to determine whether significant differences exist in primary endpoint results between subgroups. The list of subgroups (with applicable definitions in parentheses) includes, but is not necessarily limited to:

- Sex (Female vs. Male)
- BMI (Obese vs. Non-Obese)
- Age (< 65 years vs. \geq 65 years)
- Race (Black or African heritage vs. other races)
- Lead Chamber (Right Atrium vs. Right Ventricle)
- Pulse generator type (pacemaker vs. CRT-P)
- Pacing Capture Threshold Test Type (In-office vs. Auto-threshold) – applicable to Primary Efficacy Endpoint only

Female sex and minority races are considered under-represented group in most cardiovascular device clinical studies. Any efforts to maximize subject retention would be targeted to the under-represented group as well. The study's inclusion and exclusion criteria are not expected to have a negative effect on the recruitment or retention of the said populations.

A log-rank test will be performed to assess differences in Primary Safety endpoint results by subgroup. A Pearson's chi-square test will be performed to assess the differences in Primary Effectiveness endpoint results by subgroup. A test for significance at the 15% level will be performed. For each subgroup variable in which a significant difference exists, the results for each subgroup will be presented separately. BSC does not plan to seek labeling for these subgroups based on these analyses.

11.4.3. Pooling Analysis

For both primary endpoints, data from the right atrial and right ventricular leads will be pooled for analysis, based on the expected similarity in results across chambers. The assumption of poolability across chambers will be assessed through the subgroup analysis described in Section 11.4.2.

11.4.4. Multivariable Analyses

Univariable analyses of various baseline covariates and their relationship to each endpoint are outlined in Section 11.4.2. For each endpoint, all baseline characteristics found to be significantly associated with the outcome will be included as covariates in a multivariable regression model. The impact of each baseline characteristic's subgroups will be presented along with the multivariable model results.

11.4.5. Impact of Repeated Measures

As stated in Section 11.3.1, each subject in the study can contribute up to two leads to the endpoint analyses. To investigate the potential impact of repeated measures on the endpoint

results, analyses will be performed for each primary endpoint comparing a model adjusted for repeated measures to one unadjusted for repeated measures. Results from both models – accounting and not accounting for repeated measures – will be presented.

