The data to be collected during enrollment into the INGEVITY+ Study includes subject demographic data, a physical assessment of the subject, including height and weight, arrhythmia history, cardiac disease history, and current cardiovascular medications.

Implant or attempted implant of the INGEVITY+ Leads must occur ≤ 30 days of the subject signing informed consent.

10.5. *Implant Visit [Day 0]*

The IPG and INGEVITY+ leads should be implanted and tested in accordance with the Physician's Manuals. The implant procedure, peri-implant management, and post-operative care of the INGEVITY+ leads are standard of care for cardiac pacemaker and CRT-P implants. There are no special tools or procedures required to implant INGEVITY+ leads.

Subjects in this clinical study will be required to be attempted with INGEVITY+ Leads in their RA and RV. The data to be collected from the implant procedure includes:

- IPG:
 - Type
 - Manufacture
 - Model
 - Serial number
 - Pocket location
 - Device location in pocket
 - Time of pocket closure
- Leads (all attempted and successfully implanted):
 - Lead location
 - Model

- Serial number
 - Anatomical space
 - Number of turns to fully extend the helix
 - Number of turns to fully retract the helix, for repositioning if applicable
 - Voltage threshold, sensed amplitude(s), and pacing impedance of the leads measured with a pacing system analyzer (PSA)
 - Voltage threshold, sensed amplitude(s), and pacing impedance of the leads measured with the implanted IPG
- Implant accessories used:
 - Vein pick
 - Stylet
 - Stylet guide
 - Fixation tool
 - Slit Suture Sleeve

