10.9.1. Source Documentation Requirements

See Table 10-3 in Section 10.12 for required source documentation for additional follow-ups.

10.10. *Remote Follow-up*

Study follow-up visits shall be completed in-clinic; however, if it is not possible to complete an in-clinic follow-up visit (e.g., local restrictions due to global health crisis) a telephone or telehealth visit with LATITUDE remote transmission of lead measurements can be substituted. The reason for the remote follow-up visit must be documented. Subjects may be followed on the LATITUDE system from the time they are implanted. If a patient is followed on the LATITUDE system, the automatic threshold or automatic capture (TREND

or Auto) feature must be turned on for all chambers in which INGEVITY+ leads are implanted.

The subject will be contacted for a telephone or telehealth visit, within the applicable follow-up window. Any applicable adverse events, device deficiencies, and deviations that have occurred will be documented. If it is the subject's 3-month follow-up, cardiovascular medications must be assessed for any updates or changes. Any changes to the subject's cardiovascular medication must be documented.

When a LATITUDE remote transmission is performed to obtain lead measurement data for the 1-Month and/or 3-Month Follow-up visits, the following measurements of all leads are to be entered in the case report forms:

- Intrinsic amplitude (mV)
- Voltage pacing capture threshold from automatic threshold or automatic capture test (V, at 0.4 ms pulse width). Automatic threshold or automatic capture tests in the right atrium are performed in the unipolar mode lead configuration. Automatic threshold or automatic capture tests in the right ventricle and left ventricle are performed in the programmed configuration.
- Lead impedance (Ω)

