Assessment of pregnancy for women of childbearing potential: method of assessment per physician discretion	Retain at site
Documentation of: 
 Demographics: age at implant, gender, race, ethnicity Indication for implant Cardiovascular medications Subject's height and weight Arrhythmia history Cardiac disease history 	Retain at site
Implant details regarding IPG, leads, and accessories used or signed Implant Technical Source Form	Retain at site
Printout of PSA measurements and ECG strip showing loss of capture or signed Implant Technical Source Form	Retain at site
Implant questionnaire	Retain at site
For in-clinic visits: Printout of IPG measurements and threshold results (device follow-up report and ECG programmer strip documenting LOC), for all lead pacing threshold tests	Retain at site
For remote visits: Appropriate LATITUDE report or page print of LATITUDE data or signed Technical Source Form for IPG measurements and threshold results	Retain at site
Time of pocket closure, to document time 0	Retain at site
Time of pre-discharge visit to document visit window	Retain at site
PA and lateral chest X-ray or fluoroscopic image of lead distal tip fixation, either from Implant or Pre-Discharge	Retain at site
Reportable Adverse Events, Device Deficiencies, and Protocol Deviations, if applicable	Retain at site
In the event of subject death: 
 Death narrative Relevant medical records Death certificate Autopsy report 	Submit one copy to Boston Scientific RM At [contact] or uploaded to the Rave Database Retain at site

Note: If thermal paper from the device programmer is used for source documentation, signed and dated photocopies or printed pdfs should be used instead, or the strips should be electronically saved.

11. Statistical Considerations

11.1. *Endpoints*

For an INGEVITY+ lead to be eligible to contribute to endpoint analyses, it must be the final lead implanted or attempted per chamber during the initial procedure. Therefore, each subject may contribute up to two total INGEVITY+ leads to the endpoint analyses – one each for the right atrium and right ventricle. See section 11.3.1 for specifics on the analysis sets used for each endpoint analysis.

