11.1.1.2. Sample Size

A sample size of 200 leads (185 required for analysis plus 15 for attrition) is required to evaluate Primary Safety Endpoint. This sample size was calculated using the normal approximation to the binomial and confirmed via Monte Carlo simulations employing Kaplan-Meier methodology, using SAS version 9.4 with the following assumptions:

- Expected performance = 98%
- Performance goal = 93%
- Expected attrition/missing data = 7.5%
- One-sided significance level = 2.5%
- Power = 90%

The sample size for the INGEVITY+ Study is determined by this endpoint.

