11.1.2.2. Sample Size

A total of 57 measurements (3-month [contact] ms) are required to sufficiently power the Primary Efficacy Endpoint. The following assumptions were used to calculate the sample size:

- Performance goal = 80%
- Expected rate = 95%
- One-sided significance level = 2.5%
- Power = 90%

The sample size for this study was not determined by this endpoint.

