11.1.2.3. Statistical Methods

All INGEVITY+ leads with a PCT measurement taken at the 3-month visit (with a 0.4 ms pulse width) will be included in the endpoint evaluation. The number of responders (PCT at 3-month visit ≤ 2 V) divided by the total number of INGEVITY+ leads included in the endpoint evaluation will be calculated. The one-sided 2.5% binomial exact lower confidence limit will be calculated and compared to the performance goal of 80%. If the lower confidence limit exceeds 80%, the null hypothesis will be rejected.

To assess the potential impact missing data could have had on the analysis results, a tipping point analysis will be conducted that will include all implanted INGEVITY+ leads. The tipping point analysis will assign each lead with missing data as either being a PCT responder or a PCT non-responder. All possible combinations of these leads' data will be evaluated along with the actual observed data to find the point, if any, at which the endpoint is failed.

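### The PCT pass/fail limit treats a subject's two leads as independent, and the repeated-measures model in 11.4.5 has no role in the decision, so the stated 2.5% error is not protected if leads correlate more than weakly

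*Combined protocol and SAP*

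**What the plan says.** Section 10.5 sets the pairing: "Subjects in this clinical study will be required to be attempted with INGEVITY+ Leads in their RA and RV". Sections 11.1 and 11.3.1 carry it into the analysis: "each subject may contribute up to two total INGEVITY+ leads to the endpoint analyses", one per chamber.

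For PCT, 11.1.2.3 divides responding leads by all leads with a 3-month measurement. It then states: "The one-sided 2.5% binomial exact lower confidence limit will be calculated and compared to the performance goal of 80" percent. The decision follows from that limit alone: "If the lower confidence limit exceeds 80%, the null hypothesis will be rejected". The synopsis gives the same test. Section 11.1.2.2 asks for little: "A total of 57 measurements", at a performance goal of 80%, an expected rate of 95%, one-sided 2.5% and 90% power. The study is sized by safety; of that endpoint 11.1.1.2 says "The sample size for the INGEVITY+ Study is determined by this endpoint". It requires 200 leads, of which 185 are for analysis.

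The pairing is taken up in 11.4.5: "analyses will be performed for each primary endpoint comparing a model adjusted for repeated measures to one unadjusted for repeated measures". Both sets of results are to be shown. The section does not name a model, say which result governs, or say what happens if the two disagree. Poolability of the two chambers (11.4.3) is judged by the subgroup test in 11.4.2, which for PCT is a Pearson chi-square at the 15% level.

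**The concern.** A binomial exact limit guarantees its error rate only if the counted units are independent. Two leads in one subject share the patient and the pulse generator. They also share the visit mode: for a remote visit, 10.10 says that "the following measurements of all leads are to be entered in the case report forms". If non-response tends to occur in both leads of the same subject, the number of non-responding leads varies more than the binomial allows, and a device truly at 80% passes more often than 2.5% of the time.

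This is one of two primary endpoints in a study run to meet post-approval requirements. The sponsor has already identified the issue, so the plan should say in advance which result decides, rather than leave two results side by side.

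**Working it through.** **Inputs.** Goal 80%, expected 95%, one-sided 2.5% (11.1.2.2); 185 analysable leads (11.1.1.2); 105 subjects (7.1); at most two leads per subject (11.1). Rho is not in the documents and is varied from 0 to 0.5.

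**The plan's own figure.** The normal approximation for 80% vs 95% gives n = [(1.960 × √0.16 + 1.282 × √0.0475) / 0.15]² = 50.2. With continuity correction this is 56.7, so 57, as stated. The calculation has no term for pairing.

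**How many pairs.** If 105 subjects give 185 leads with data, at least 185 − 105 = 80 give two. The most paired layout is 92 pairs plus one single lead.

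**Planned cut-off.** With 185 leads, the Clopper-Pearson lower limit is 80.09% at 26 non-responders and 79.48% at 27. The rule therefore passes at 26 or fewer.

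**False-pass rate.** Let q = 0.20 be the non-response rate. For a pair, P(both fail) = q² + rho × q(1 − q) = 0.04 + 0.16 × rho. The mean count is 37. Its variance is 185 × 0.16 + 2 × 92 × 0.16 × rho = 29.6 + 29.44 × rho, so the standard deviation rises from 5.44 at rho 0 to 6.20 at rho 0.3. Summing the exact distribution up to 26 gives, at a true 80%:

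| rho | 0 | 0.1 | 0.2 | 0.3 | 0.5 |
|---|---|---|---|---|---|
| Planned, 92 pairs + 1 | 2.3% | 2.9% | 3.5% | 4.1% | 5.3% |
| Planned, 80 pairs + 25 single leads | 2.3% | 2.8% | 3.3% | 3.8% | 4.9% |
| Clustered limit, 92 pairs + 1 | 2.1% | 2.2% | 2.3% | 2.3% | 2.2% |

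The clustered limit is Clopper-Pearson with effective n = n / [1 + rho × (Σm²/Σm − 1)], where m is leads per subject and rho is estimated from the pairs and floored at 0. For 92 pairs plus one, Σm²/Σm − 1 = 369/185 − 1 = 0.995. An estimated rho of 0.2 then gives an effective n of 185/1.199 = 154.

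**Dependence on the lead count.** Slack in the exact limit changes with n. Of the 25 counts from 176 to 200, the number with a false-pass rate above 2.5% is 0 at rho 0, 6 at 0.05, 10 at 0.1, 19 at 0.15, 23 at 0.2 and 25 at 0.25. The crossing lies between rho 0.001 (190 leads) and about 0.21 (184 leads); at 185 leads it is about 0.03.

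**Away from 80%.** At a true 95% the planned rule passes with probability above 99.9% for every rho from 0 to 1. At rho 0.3 and a true 79% the pass rate is 2.1%.

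**Chamber check (secondary).** With 93 pairs and both chambers at 95%, the chi-square at nominal 15% has size 16.1, 13.9, 11.7 and 9.4% at rho 0, 0.1, 0.2 and 0.3. Mid-p McNemar has 14.1, 13.9, 13.7 and 13.4%. For 92% vs 98%, power is 71, 72, 73 and 74% for the chi-square and 68, 72, 76 and 81% for mid-p McNemar.

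**The case against.** The strongest reply is that nothing in the documents places rho above weak. Shared visit mode makes positive correlation plausible but does not measure it. Section 10.10 even weakens the argument: remote atrial thresholds are taken in unipolar mode and ventricular ones in the programmed configuration, so a remote subject's two leads need not share a test mode. This stands, and it is why the result is given as a range.

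The excess is also a boundary effect. It has largely gone one percentage point below the goal, and it shrinks if the chambers differ: at 70% and 90% (average 80%), false-pass is 2.46% at rho 0.1 and 2.93% at rho 0.2. No change of decision is likely if the lead performs as expected. This stands too, but the goal is exactly where the 2.5% is defined.

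Three stronger readings are tempting and not supported. A reader might infer that the plan ignores pairing; 11.4.5 does address it, and the gap is only the missing decision role and model. A reader might infer that the safety error is inflated as well; with the log-log limit, no censoring and rho 0.2, the false-pass rate at 93% is 1.5% with 186 leads and 2.8% with 190, so the direction depends on the cut-off and no such claim is made. A reader might infer that the unpaired chamber test is likely to miss a real difference; its own power does not fall as rho rises, it is merely less efficient than a paired test from about rho 0.2, and 11.4.2 attaches only separate presentation to a significant result.

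Finally, 11.4.6 refers to an SAP approved before analysis. If that document already sets a clustered PCT limit, only the protocol wording needs aligning.

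**Conclusion.** The point holds in a limited form. The PCT decision rests on an independent-lead limit, and the side-by-side presentation in 11.4.5 does not protect the stated 2.5%. For assumed rho of 0.1 to 0.5 the false-pass rate at a true 80% with 185 leads is about 2.9% to 5.3%; by rho 0.25 every lead count from 176 to 200 exceeds 2.5%. This rests on positive correlation, on nearly complete pairing and on both chambers being at 80%. It has no practical effect if the true rate is near 95%. The change is worth making because it is cheap and the endpoint has leads to spare (57 needed, 185 planned). The chamber test is a secondary matter.

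**What to change.** In 11.1.2.3 and 11.4.5, prespecify one subject-clustered lower limit as the PCT decision limit, and report the independent-lead Clopper-Pearson limit as sensitivity. One workable choice among several is the effective-sample-size limit shown above. Estimate rho over pairs as mean[(y1 − q)(y2 − q)] / [q(1 − q)], where y1 and y2 are the non-response indicators (1 or 0) of a subject's two leads and q is the pooled non-response rate. Floor it at 0, and set it to 0 when there are no non-responders, so that the limit always exists and then equals the planned one.

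The change is wording only: no new data, no extra leads, and the safety decision is untouched. The price is a wider limit. Power with 185 leads at a true 90%:

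| rho | 0 | 0.1 | 0.2 | 0.3 |
|---|---|---|---|---|
| Planned limit | 97.0% | 96.4% | 95.7% | 95.1% |
| Clustered limit | 96.5% | 94.5% | 92.3% | 89.8% |

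At the expected 95%, power stays at 99.97% or more up to rho 0.3.

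Optional, in 11.4.2 and 11.4.3: report a mid-p McNemar test on subjects with both leads measured alongside the chi-square for PCT, with the number of leads lacking a partner. It has no power advantage below about rho 0.1 to 0.2 and is slightly worse at rho 0.
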